23.10 Adverse Event Reporting Chart

24.0 APPENDIX B - Data Safety and Monitoring Plan (DSMP)

24.1 Brief Study Overview

The Primary Objective of the CTN-0067 CHOICES scale-up study is to compare the effectiveness of HIV clinic-based XR-NTX in decreasing substance use and increasing HIV viral suppression in HIV-infected participants with opioid use disorder to treatment as usual (TAU) in this population. Details for the definitions and reporting of safety events are found in the protocol (Appendix A).

24.2 Oversight of Clinical Responsibilities

24.2.1 Site Principal Investigator

Each participating site's PI is responsible for study oversight, including ensuring human research subject protection by designating appropriately qualified, trained research staff and medical clinicians to assess, report, and monitor adverse events.

Regarding safety, all Adverse Events (AEs) occurring during the course of the clinical trial will be collected, documented, and reported by the investigator or sub-investigators according to the protocol. The assessment of Adverse Events (medical and/or psychiatric) will commence at the time of participant consent and will continue through 30 days post last active treatment visit.

The occurrence of AEs and Serious Adverse Events (SAEs) will be assessed at each clinic visit during the study. Serious adverse events will be followed until resolved or considered stable, with reporting to the CCC Safety Monitor/Medical Monitor through the follow-up period.

Standard reporting, within 7 days of the site becoming aware of the event, is required for reportable AEs. Expedited reporting (within 24 hours of their occurrence and/or site's knowledge of the event) is required for reportable SAEs (including death and life-threatening events).

24.2.2 Medical Monitor/Safety Monitor

The NIDA Clinical Coordinating Center (CCC) Medical Monitor/Safety Monitor is responsible for reviewing all adverse events and serious adverse events reported. All SAEs will be reviewed at the time they are reported in the EDC. The Medical Monitor will also indicate concurrence or not with the details of the report provided by the site PI. Where further information is needed, the Medical Monitor/Safety Monitor will discuss the event with the site. Reviews of SAEs will be conducted in the Advantage eClinical data system and will be a part of the safety database. All AEs are reviewed on a regular basis to observe trends or unusual events.

Reports will be generated and presented for Data Safety Monitoring Board (DSMB) meetings. The DSMB will receive listings of AEs and summary reports of all SAEs at a frequency requested by the DSMB, but at least annually. Furthermore, the DSMB will be informed of expedited reports of SAEs.

24.2.3 Data and Safety Monitoring Board (DSMB)

The NIDA CTN DSMB affiliated with this trial will be responsible for conducting periodic reviews of accumulating safety, trial performance, and outcome data. The DSMB will make recommendations to NIDA as to whether there is sufficient support for continuation of the trial, evidence that study procedures should be changed, or evidence that the trial (or a specific site)

should be halted for reasons relating to safety of the study participants or inadequate trial performance (e.g., poor recruitment).

Following each DSMB meeting, the NIDA CCTN will communicate the outcomes of the meeting, based on DSMB recommendations, in writing to the study Lead Investigator. This communication detailing study safety information will be submitted to participating IRBs.

24.2.4 Quality Assurance (QA) Monitoring

The monitoring of the study site will be conducted on a regular basis using a combination of NIDA CCC contract monitors and the local Node QA monitors. Investigators will host periodic visits for the NIDA CCC contract monitors and Node QA monitors. The purpose of these visits is to assess compliance with GCP requirements and to document the integrity of the trial progress. Areas of particular concern will be the review of Inclusion/Exclusion criteria, participant Informed Consent Forms, protocol adherence, safety monitoring, IRB reviews and approvals, regulatory documents, participant records, study drug accountability, and Principal Investigator supervision and involvement in the trial. The Monitors will interact with the sites to identify issues and re-train the site as needed to enhance research quality.

QA Site Visit Reports will be prepared by the NIDA CCC contract monitors following each site visit. These reports will be forwarded to the site Principal Investigator, the study Lead Investigator and NIDA.

24.2.5 Management of Risks to Participants

24.2.5.1 Confidentiality

Confidentiality of participant records will be secured by the use of study codes for identifying participants on CRFs, secure storage of any documents that have participant identifiers, and secure computing procedures for entering and transferring electronic data. No identifying information will be disclosed in reports, publications or presentations.

24.2.5.2 Information Meeting Reporting Requirements

The consent form will specifically state the types of information that are required to be reported and the fact that the information will be reported as required. These include suspected or known sexual or physical abuse of a child or elders, or threatened violence to self and/or others.

24.2.5.3 Human Subject Protection

The study medical clinician will evaluate all pertinent screening and baseline assessments prior to participant randomization to ensure that the participant is eligible and safe to enter the study. Adverse events (AEs) and concomitant medications will be assessed and documented at each clinic visit. Individuals who experience an AE that compromises safe participation will be discontinued from further medication administration and provided referrals for other treatment or to specialized care. Study personnel will request that the participant complete an end of study visit to assure safety and to document end of treatment outcomes.

24.2.5.4 Pregnancy

Pregnancy is an exclusion criterion for study participation. A positive pregnancy test post-randomization will result in the cessation of study medication. Participants who discontinue medications will be expected to continue with study visits. Pregnancy test results and related outcome information will be collected on a Pregnancy and Outcome CRF. The site staff will follow the participant until an outcome of the pregnancy is known.

24.2.5.5 Study Specific Risks

XR-NTX blocks the effects of exogenous opioids after administration. After treatment, participants are likely to have reduced tolerance to opioids. Following Vivitrol® treatment, opioid use at the end of a dosing interval or after missing a dose could result in potentially life-threatening opioid intoxication (involving respiratory compromise or arrest, circulatory collapse, etc.) Attempting to overcome the blockade effects of Vivitrol® by administering large amounts of exogenous opioids is associated with potential risk of opioid overdose. Participants in this study will receive an information card that will notify clinicians that they are receiving XR-NTX as part of a research study.

24.3 Data Management Procedures

This protocol will utilize a centralized Data and Statistics Center (DSC). A web-based distributed data entry model will be implemented. This electronic data capture system (Advantage eClinical) will be developed to ensure that guidelines and regulations surrounding the use of computerized systems in clinical trials are upheld.

24.4 Data and Statistics Center Responsibilities

The DSC will: 1) develop and apply data management procedures to ensure the collection of accurate and good-quality data, 2) provide source documents and electronic Case Report Forms (eCRFs) for the collection of all data required by the study, 3) develop data dictionaries for each eCRF that will comprehensively define each data element, 4) prepare instructions for the use of Advantage eClinical and for the completion of eCRFs, 5) conduct ongoing monitoring activities on study data collected from all participating sites, and 6) perform data cleaning activities prior to any interim analyses and prior to the final study database lock.

24.5 Data Collection and Entry

Data will be collected at the study sites on source documents and entered by the site into eCRFs in Advantage eClinical, or will be collected via direct entry into the eCRF. In the event that Advantage eClinical is not available, the DSC will provide the sites with paper source documents and completion instructions. Data will be entered into Advantage eClinical in accordance with the instructions provided during project-specific training and guidelines established by the DSC. Data entry into the eCRFs shall be performed by authorized individuals. Selected eCRFs may also require the investigator's electronic signature.

The investigator at the site is responsible for maintaining accurate, complete and up-to-date research records. In addition, the investigator is responsible for ensuring the timely completion of eCRFs for each research participant.

24.6 Data Monitoring, Cleaning and Editing

eCRFs will be monitored for completeness and accuracy throughout the study. Dynamic reports listing missing values and forms are available to sites at all times in Advantage eClinical. These reports will be monitored regularly by the DSC. In addition, the DSC will identify inconsistencies within eCRFs and between eCRFs and post queries in Advantage eClinical on a scheduled basis. Sites will resolve data inconsistencies and errors by entering all corrections and changes directly into Advantage eClinical. As described above, the CCC will conduct regular visits to sites, during which audits comparing source documents to the data entered on the eCRF will be performed. Any discrepancies identified between the source document and the eCRF will be corrected by the site.

Trial progress and data status reports, which provide information on recruitment, availability of primary outcome, treatment exposure, attendance at long term follow-up visits, regulatory status, and data quality, will be generated daily and posted to a secure website. These reports are available to the site, the corresponding local Node, the Lead Investigator, the coordinating centers, and NIDA, to monitor the sites' progress on the study.

24.7 Database Lock and Transfer

At the conclusion of data collection for the study, the DSC will perform final data cleaning activities and will “lock” the study database from further modification. The final analysis dataset will be returned to NIDA, as requested, for storage and archive.

25.0 APPENDIX C - “Random Assignment Bootstrapping”

CTN-0055 to estimate likely power for CTN-0067

It is harder to calculate power for a repeated-measures or time series approach than it is for an approach that just uses data from a single time point. The reason is that, for the time series approach, the model needs the entire time series, not just the concluding data point. **Table 1** contains a (partial) list of the parameters necessary to generate realistic data for the proposed scale-up study.

25.1 Table 1: Some Parameters Necessary to Simulate Realistic Data for CTN-0067

Design Parameters

- total sample size
- number and spacing of time points
- number of sites

States of Nature

- autocorrelation of suppression indicator
- monthly probability of death
- monthly probability of loss to follow-up
- monthly probability of going off treatment, ntx arm
- monthly probability of going off treatment, tau arm
- probability of initiation on ntx arm
- probability of initiation on tau arm
- monthly probability of suppression in (ntx, tau)
- standard deviation of site effect -- perhaps in (ntx, tau)

Although the first 3 of these are design parameters, thus controlled by the investigators, the remainder are states of nature that need to either be assumed or be estimated (with attendant noise) from a pilot study with 51 participants. This list implicitly embodies various simplifying assumptions that may or may not be true. For example, it could be that the probability of dropout depends on whether the participant is or is not suppressed, whether the participant is alcohol-dependent in addition to opioid-dependent, and even which site the participant comes from.

There is an alternative approach that, while it has its own problems, avoids the necessity of explicitly estimating many parameters from few observations and making implicit simplifying assumptions. Instead, we propose to perform the power calculation by bootstrapping data from the pilot study.

This works because, when calculating power for a non-inferiority design, the conventional approach is to calculate it under the alternative hypothesis that the two treatments are the same.

This is accomplished in the simulation by first pooling the two arms of the pilot (i.e., ignoring the treatment arm), then bootstrapping data from the pool, and finally randomly assigning the bootstrapped observations to the two treatment arms. We call this approach, in which a bootstrap sample is drawn and then treatment is randomly assigned to the bootstrapped observations, **“Random Assignment Bootstrapping.”**

As remarked above, the Random Assignment Bootstrap approach has its own limitations. Some arise from the small size of the pilot study. Others have to do with differences in pilot study and scale-up designs. Specifically, the proposed scale-up will have VL visits at months 0, 3, and 6, with the primary suppression outcome being assessed at M6. The pilot study had visits at months 0, 1, 2, 3, and 4, but in this simulation we use only visits 0, 2, and 4 to assess the outcome at M4. The pilot study design is less powerful than the scale-up will be because although it has the same number of visits, they are temporally closer together. Also, if there is an outcome difference between arms in CTN0055, random assignment bootstrapping will probably over-estimate the within-arm variance, leading to a smaller power estimate. For these reasons, scale-up power is expected to exceed the power calculated by Random Assignment Bootstrapping of the pilot study.

The power calculations are performed only for the members of the opiate-only + overlap group who are unsuppressed at baseline. There are only 9 participants in this group, with suppression status values at the various visits as given in Table 2.

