17.7 Rationale for Sample Size

Figure 4 shows the non-inferiority margin required for power of (0.8, 0.9) (using the lower tail of the two-sided 95% confidence interval) as a function of the sample size for the non-inferiority test of XR-NTX versus TAU at 4 months, as estimated from data “random-assignment-bootstrapped” from the (opioid + overlap) group who were unsuppressed at baseline in the pilot study (CTN-0055). There are only 9 participants in the bootstrap population: 7 in Core and 2 in UBC. The random-assignment bootstrap approach was used at 4 months as a conservative way to estimate power in the scale-up (see appendix). The margin is expressed in terms of the risk ratio (RR), that

is, $\Pr(\text{suppressed} \mid \text{XR-NTX}) / \Pr(\text{suppressed} \mid \text{TAU})^1$. A horizontal reference line in **Figure 4** marks $\text{RR} = 0.75$, and vertical reference lines mark the intersection of the horizontal line with the power curves for $(0.8, 0.9)$. The vertical lines intersect the N axis at sample sizes of about $(350, 480)$. For a given sample size, use of a margin at or below the one specified by the relevant curved line will grant power in excess of that depicted by the line. For example, an RR margin less than or equal to 0.75 will grant a power of at least 90% for total sample size (both arms together) of about 480 , and will grant a power of at least 80% for total sample size of 350 . We have chosen this last point upon which to base our sample size.

This particular example is calculated using the Rose et al. binary RMVL model. The fixed effects in the model are treatment, visit number (continuous), time by treatment interaction, baseline alcohol, and site (categorical). The data for each participant are assumed to have an exchangeable correlation structure. Missing data are assumed to be unsuppressed. Note that cases in which the model failed to converge or converged but SAS flagged the result as questionable have been dropped from this analysis. The number of analyzed iterations was $(9020, 9492, 9696, 9819, 9848, 9869, \text{ and } 9911)$ for $n = (200, 250, 300, 350, 400, 450, 500)$, respectively. With the assumptions above, a non-inferiority sample size calculation was performed using commercial software PASS and got very similar results.

17.7.1 Figure 4. Non-inferiority margins granting power = 0.8 and 0.9 as a function of sample size

Additional Comments Concerning Choice of RR margin

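### Section 17.1's unadjusted 95% limit conflicts with the O'Brien-Fleming-type boundary in 17.11, and Appendix C's two reasons for expecting more power than calculated do not apply to the planned test

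*Combined protocol and SAP*

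**What the plan says.** **Decision rule.** Section 17.1 rejects inferiority if the lower 95% confidence limit of the suppression ratio (XR-NTX over TAU) is above 0.75. Section 17.7 computes power at the lower tail of the two-sided 95% interval, so at z = 1.96. Section 17.11 starts efficacy monitoring only after one third of participants have 24-week data and the sample size has been re-estimated. If the size is unchanged, it then looks at every later DSMB meeting with an O'Brien-Fleming-type boundary at one-tailed 0.025. Section 19.1 says the DSMB meets at least annually. No section gives an adjusted final critical value or confidence level.

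**Power.** Section 17.7 reports at least 80% power at N = 350 and states: "The random-assignment bootstrap approach was used at 4 months as a conservative way to estimate power in the scale-up". Appendix C gives two reasons. The first is spacing: the pilot design is "less powerful than the scale-up will be because although it has the same number of visits, they are temporally closer together". The second is pooling: if the pilot arms differ, "random assignment bootstrapping will probably over-estimate the within-arm variance, leading to a smaller power estimate". It then concludes: "For these reasons, scale-up power is expected to exceed the power calculated by Random Assignment Bootstrapping of the pilot study".

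**Planned test.** Section 17.2 specifies a log-link GEE with months 3 and 6, linear month, treatment-by-month, alcohol and site terms, exchangeable correlation and a month-6 contrast.

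**The concern.** Two statements in the plan would mislead whoever applies them. First, the final analysis has two thresholds. An analyst following 17.1 and one following 17.11 could read the same result differently, and using 17.1 after efficacy looks puts the one-sided error above the 0.025 that 17.11 states. This has to be settled before unblinded looks begin.

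Second, Appendix C tells the reader that the calculated 80% is on the low side. That comfort rests on a spacing argument and a variance argument. If neither applies to the contrast and scale being tested, readers and the DSMB are given a margin of safety that has not been shown.

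**Working it through.** **The plan's own figure.** The bootstrap cannot be rerun: Appendix C's Table 2, which should hold the visit-level values, was not in the text available to me. A closed form gives the scale. Inputs: margin 0.75 (17.1), 175 per arm, equal arms (Appendix C: "calculate it under the alternative hypothesis that the two treatments are the same"), one-sided 0.025.

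Power = Φ(0.28768/SE − 1.96), with SE² = 2(1−p)/(175p) and 0.28768 = −ln 0.75.

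- p = 5/9 (17.7's pilot table, 3 + 2 of 9): SE = √(1.600/175) = 0.0956; power 85%.
- p = 0.573 (the BHIVES rate in 17.6): power 88%.
- 80% at N = 350 corresponds to p of about 0.52.

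The 5/9 uses last non-missing status, whereas in the simulation "Missing data are assumed to be unsuppressed", so the bootstrap rate need not equal 5/9. The 80% is neither confirmed nor refuted.

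**Decision rule.** Assumptions, because the documents leave look times open: Lan-DeMets O'Brien-Fleming-type spending at one-sided 0.025; uniform enrolment over 22 months; outcome about 5.5 months after randomization; re-estimation at month 13; first look at a later meeting. The information fraction at month m is (m − 5.5)/22, giving 0.48, 0.61, 0.75 and 0.89 at months 16, 19, 22 and 25.

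| Schedule | Looks before final | Final z | One-sided error if 1.96 is kept | Power of an 80% design with the correct boundary |
|---|---|---|---|---|
| One look | 0.61 | 1.983 | 2.62% | 79.6% |
| Annual | 0.89 | 2.050 | 2.86% | 79.1% |
| Six-monthly | 0.61, 0.89 | 2.060 | 2.90% | 78.9% |
| Quarterly | 0.48, 0.61, 0.75, 0.89 | 2.07 | 2.94% | 78.6% |

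A single very early look (0.33) would leave the final value at 1.961, with no practical effect.

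**Spacing.** Going from months (2, 4) to (3, 6) multiplies month by 1.5. The month and interaction coefficients are divided by 1.5, so the last-visit contrast is the same: β + 4θ in one coding equals β + 6θ in the other. Fitting the 17.2 model (alcohol and eight-site terms) to one simulated data set of 350 gave log RR 0.12734, SE 0.11529 under both codings.

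Weaker real correlation between visits that are further apart does not help either. With two visits and treatment-by-month, the model is saturated in arm and time. Without covariates and with missing values filled in, the contrast is the last-visit log RR with its usual SE, whatever the correlation. With an alcohol term, a 50% last-visit rate and 3,000 runs each, correlations of 0.1, 0.3, 0.5 and 0.7 gave a mean SE of 0.107 every time (closed form 0.1069) and power of 75.7, 76.2, 76.0 and 76.0%.

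**Pooling.** On the log RR scale, n × variance = (1−p₁)/p₁ + (1−p₂)/p₂. Since (1−p)/p is convex, pooling cannot raise this sum.

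- Unpooled 60%/50%: 0.4/0.6 + 0.5/0.5 = 1.667.
- Pooled at 0.55: 2 × 0.45/0.55 = 1.636.
- Pooled at 5/9: 2 × (4/9)/(5/9) = 1.600.
- On the p(1−p) scale: 0.2475 pooled against (0.24 + 0.25)/2 = 0.2450, a rise of 1.0%.

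The stated direction holds only on the last scale, which is not the one tested. Under equal arms, what matters is the common rate: the sum is 1.333 (power 91%) if both arms are at 60%, and 2.000 (power 77%) if both are at 50%.

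**The case against.** The strongest objection concerns spacing. Appendix C says "in this simulation we use only visits 0, 2, and 4", so visit 0 may have been in the simulated model. With three visits the linear-month model is not saturated, and correlation does matter. With visit 0 all unsuppressed, then 40% and 50%, the SE is 0.106 at correlation 0.7 and 0.097 at 0.1, with power of about 79% and 85%. If wider spacing weakens correlation, the first reason works in that model. This stands as far as it goes, but 17.2 analyses two time points, so it does not carry over to the planned test.

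A later visit could also raise power through a higher suppression rate. Section 6.3, which says the outcome needs at least six months, may support this. Appendix C does not argue it and gives no rates.

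On variance, Appendix C is hedged and correct for p(1−p). It goes wrong in carrying this to power on the log RR scale.

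On the decision rule, 17.11 already fixes the boundary, the effect is small, and the upper figures need quarterly meetings where 19.1 promises only annual ones. All true; but 17.1 still states a different rule.

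The plan discloses the nine participants, schedules a re-estimation and reports similar results from commercial software. These bear on the 80% itself. They do not repair the direction claim or reconcile the two thresholds.

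**Conclusion.** Both parts are wrong as written, and both are modest.

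1. Sections 17.1 and 17.11 give different final thresholds once an efficacy look has been taken. Under the assumed schedules the final boundary is about 1.98 to 2.07, and keeping 1.96 gives one-sided error of about 2.6 to 2.9%. The size depends on the number and timing of looks.
2. Appendix C's two reasons do not support higher power for the 17.2 test. Spacing has no effect on the two-visit contrast, and pooling works slightly in the opposite direction on the scale tested.

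A reader might infer that the trial has less than 80% power. The documents do not support that: failed reasons for optimism are not evidence of a shortfall, and the printed rates give 85 to 88% in the closed form. Nor can it be said that the plan withholds the suppression rate behind the 80%, since Table 2 should hold the visit-level values. The 17.11 boundary itself is not in question.

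**What to change.** - **17.1:** replace the fixed lower 95% limit by the lower limit at the one-sided level left by the 17.11 boundary after the efficacy looks actually taken.
- **17.7:** say that the quoted power is before this adjustment, and do not rest the label conservative on Appendix C's two reasons.
- **Appendix C:** delete the two reasons and the sentence expecting higher power. If the real reason is a higher suppression rate at month 6 than at month 4, state it with the rates.

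The cost is text only. Sample size, model, margin and the 17.11 boundary are unchanged. The 0 to 1.4 points of power (80% down to as little as 78.6%) are already implied by 17.11.
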